7.2.2 Study Visit 1: Screening Visit

Pre-screening will take place in the Penn State Hershey MIGS clinic or over the phone with women identified as potential candidates for study participation via prior clinic visits. If the subject meets all pre-screening criteria, she will return for a screening encounter and undergo informed consent prior to any study procedure. The subject will be given ample time to ask questions or voice concerns about the study.

A detailed history and physical exam will be performed, particularly to assess for concomitant use of anti-epileptic drugs and or underlying risk of liver dysfunction. We will need approximately 8-10 cc of blood (approximately 2 teaspoons).

- 1. Liver function tests (LFTs) will be drawn.
- 2. Baseline CBC and BMP will be drawn.
- 3. Screening urine toxicology will also be performed to confirm no recent THC use.
- 4. Urine pregnancy test will be collected.
- 5. Pain medication and narcotic usage from the prior month will be assessed.
- 6. Suicidal ideation will be assessed via the Columbia-Suicide Severity Rating Scale (C-SSRS).

If the subject is found to be pregnant, have evidence of underlying hematologic/ urologic/ hepatobiliary dysfunction or a positive urine toxicology for recent THC use, the subject will be excluded.

Current medication usage will be reviewed thoroughly with special attention paid to Cytochrome P450 (CYP) inducers and inhibitors as well as Substrates of uridine 5'-diphosphoglucuronosyltransferase (UGT). If the subject is screened into the study, their condition and corresponding medication will be recorded throughout the study. Please refer to Section 10 Risks, Drug Interactions, for additional guidelines.

Baseline survey data will be collected and entered into the RedCap secured database. This information will include the WERF EPHect Questionnaire.

At this time subjects will be set up for emails to complete VAS scores directly into RedCap. If not done already, the subject will be transitioned to norethindrone acetate to start taking immediately and given instruction on how to complete the VAS scores and study questions. It will be explained to the patient that she must complete 5 out of 7 days of surveys to be enrolled into the study. If the subject is unable to complete the 5 out of 7 days, the subject will be given one additional week to determine if compliance is attainable. If the subject is unable to do so, they will screen fail.

7.2.3 Study Visit 2 – Enrollment Visit

The subject will be scheduled for a randomization/enrollment 1-2 weeks after the screening visit. The randomization will be double blind and 1:1:1. The patient will have been expected to be on norethindrone acetate (NETA) for 30 days prior to the enrollment visit. Dosing for norethindrone acetate will start at 5mg oral daily, but may be adjusted from 2.5 mg to 15 mg depending on the subject's needs to achieve amenorrhea as this standard treatment for endometriosis or to increase compliance by reducing side effects. The study team will be responsible for adjusting dosages at subsequent study visits 3 and 4. At this visit, the subject will be randomized into Group A, Group B, Group C by IDS as long as the subject has met all the criteria for enrollment. The groups are listed below:

Group	Treatment
А	Norethindrone acetate + Placebo (Hemp Seed Oil)
В	Norethindrone acetate + low dose CBD (10mg sublingual daily)
С	Norethindrone acetate + high dose CBD (20mg sublingual daily)

The subject will be given a 4 week supply of (1) placebo (2) low dose CBD or (3) high dose CBD product and instructed on its application. The subject will also receive a 4 week supply of norethindrone. Refer to the following:

- a. In the morning, take the norethindrone acetate orally with a sip of water at approximately the same time each day. This can be taken on an empty or full stomach.
- b. Prior to bed, you will administer the study drug.
 - 1. Please refrain from eating (drinking is permissible) 60 minutes prior to administration.
 - 2. Place 4 drops of the study drug under your tongue.
 - 3. Hold the study drug under the tongue for 60 seconds. After that time, swallow any remaining drug.
 - 4. Repeat steps 2 and 3 for a total of 8 drops.

Please avoid eating, drinking or smoking for 2 hours after administration.

A focus group was conducted to determine the optimal route of administration of the study drug. 1 application of 8 drops of the study drug versus 2 applications of 4 drops were compared and it was determined that the latter method was preferred.

Subjects will be instructed to take ibuprofen as first line treatment and acetaminophen if additional pain relief is needed, both of which are available over the counter. Only if requested will a stronger medication be prescribed, such as oxycodone. If needed, the subject will be advised to take first the ibuprofen 600mg every 6 hours as needed for pain with food, then acetaminophen 500-1000mg every 8 hours as needed for pain. For breakthrough pain, patients will need to contact the study team and they will be given a prescription for oxycodone 5mg oral every 6 hours as needed. As the pain associated with endometriosis tends to be cyclical, even if

the patient reports the pain as mild at the enrollment visit, they may suffer from an endometriosis flare requiring short term opioid use. Refill prescriptions for opioid pain medications will be provided beyond the screening visit on an as needed basis and will not be routinely provided at any subsequent study visits unless there is a documented need.

At the enrollment visit, baseline study surveys and VAS scores will be collected and entered into the RedCap secured database. The will have inflammatory markers drawn at this visit (1 teaspoon, <5cc of blood)

Daily Diaries:

The subjects will be instructed as to how to complete their daily diaries directly into REDCap. They will enter daily VAS scores. They will be assessed as to their adherence of the study drug. We will document the daily use of any rescue analgesic medications and menstrual pattern.

Physical Assessment

A physical assessment will be performed at visits #2-5, following the detailed history and physical examination performed at the screening visit. This assessment will include, but is not limited to:

- 1. Vitals signs (blood pressure, pulse, O2; orthostatic assessment to be done only as indicated)
- Detailed, but directed review of systems that will include symptoms concerning for liver disease, stroke, new/worsening migraine, deep venous thrombosis (DVT), pulmonary embolism (PE). This review of systems will include an assessment of (new onset) visual abnormalities.
- 3. Directed physical exam as indicated from the ROS, including an examination of the oral cavity to assess for lesions/sores
- 4. Adverse event assessment. Please refer to Section 3.3.1
- 5. Review of concomitant medications

Patient Education:

Patient will be educated on possible adverse events and concerning symptoms. If they have any of the following, they will be advised to stop the medications and contact the study investigator and/or the clinician on call to determine if they require a formal assessment: (1) Shortness of breath or difficulty breathing (2) chest pain (3) visual changes (4) persistent headache (5) severe abdominal pain (6) extensive mouth sores (7) persistent dizziness or lightheadedness (8) unilateral calf pain

Patients will be educated about the symptoms and signs of a DVT/PE and ways to reduce this risk.

Patients will also be educated about the risks of unintended pregnancy as described in the informed Consent. At the time of informed consent, the following will be reviewed with the subject:

Although norethindrone at certain dosages is approved for the indication of contraception. At the dosages this study will use, it is not indicated for this use. Therefore, you will be required to use an acceptable form of contraception during this study unless:

- 1. You have had both of your tubes tied
- 2. Have sex with a man who had a vasectomy at least 6 months ago
- 3. If you do not have sex with men
- 4. You have had a hysterectomy (removal of your uterus)

Acceptable methods include:

- 1. Male Condom: Use prior to intercourse. If using lubricant, choose a water soluble or silicone based as an oil-based lubricant can break down latex condoms.
- 2. Female Condom: Can be inserted up to 6 hours prior to intercourse; it is acceptable to use with lubricants and latex allergies.
- 3. Diaphragm with spermicide: Insert into the vagina so that it covers the cervix. Place spermicide on the diaphragm and around the edges prior to insertion. (Fitted by a healthcare provider)
- 4. Cervical cap with spermicide: Similar to the diaphragm, but smaller. Avoid this method if you have delivered a baby, as it is much less effective.
- 5. Vaginal sponge that contains a spermicide: Insert into the vagina before intercourse. Avoid leaving in the vagina for a prolonged period of time > 24 hours. Avoid this method if you have delivered a baby, as it is much less effective.
- Copper IUD, Progesterone IUD No methods above are 100% effective at preventing unintended pregnancy even with perfect use.

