3.3 Early Withdrawal of Subjects

3.3.1 Criteria for removal from study

Subjects will be removed from the study for safety reasons. Subjects will be evaluated for potential negative reactions to study medications at each visit. Additionally, subjects will be advised to contact the study team immediately with any new negative symptoms.

Known severe adverse events of the study drugs will result in the immediate cessation of the study drugs and removal from the study.

- 1. Severe adverse events of NETA include:
 - a. (1) Stroke (2) Deep Vein Thrombosis (3) Pulmonary Embolism (4) Myocardial Infarction (5) Retinal Vein Thrombosis.
 - b. Worsening or persistent migraines will result in cessation of the study drug and therefore, removal from the study.
- 2. Serious adverse events associated with CBD include:
 - a. (1) Suicidal ideation (2) Liver Dysfunction resulting in hepatic failure, hepatic pain that limits self-care activities of daily living, or acute liver damage as measured by LFTS (elevations in ALT or AST > 3 times the ULN and for ALP or TBL > 2 times the ULN)

In the case of an inadvertent pregnancy, the study participant will be immediately withdrawn from the study.

Other adverse events will be monitored and may result in cessation of the study drug and subject withdrawal from the study as determined by the clinical investigator. When possible, we will use the definitions described by the NIH's Common Terminology Criteria for Adverse Events (CTCAE), Version 5, subjects meeting criteria for a Grade 3 CTCAE will be withdrawn from the study if they can be attributed to the study drug. If causality cannot be determined, it will be attributed to the study drug.

Examples:AnemiaGrade 3Hb < 8.0	DiarrheaGrade 3Increase of \geq 7 stools per day over baseline

Withdrawal of consent at any time during the study period will also constitute the withdrawal of a study subject.

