9.2 Data that are reviewed

Adverse events are defined as unfavorable medical changes that occur during or after the study initiation, that may or may not be related to or caused by study participation. The intensity of the event will be evaluated and recorded as one of the following:

- (1) Mild intensity events may or may not be volunteered by the patient. The patient is aware of the event but it is easily tolerated.
- (2) Moderate intensity signifies discomfort sufficient to interfere with normal activities. A change in therapy may or may not be indicated.
- (3) Severe intensity side effects are almost always brought up by the patient, definitely interfere with functioning, and require a medical intervention.

The study team will be required to assess for adverse events throughout study. In general, this will require a description of the event in sufficient detail to allow for a complete medical assessment of the case and independent determination of possible causality. Information on other possible causes of the event, including concomitant medications and illnesses, must be provided. The investigator's assessment of causality must also be provided. The certainty of the relationship of the event to study participation will be recorded as "Possible Related" or Not Possibly Related." The situation surrounding the event should be assessed to determine whether it is related to the study.

Please refer to Section 3.3.1. Criteria for Removal from Study

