10.0 Risks

Cannabidiol is generally well tolerated with a good safety profile. In clinical trials, a wide range of oral dosages have been used ranging from 1.5-800mg/day.¹⁰

Common risks of Cannabidiol include decreased appetite, somnolence, fatigue, sleep disorder (insomnia), diarrhea, hypersensitivity reactions (rash), infection and liver dysfunction. Because trials are conducted under widely varying conditions, the adverse events observed in one trial cannot be directly compared to the rates in our trial or in observed practice.

Cannabidiol has been associated with dose related elevation of liver transaminases; these effects typically took place within the first 2 months of treatment. Resolution occurred in one third of patients with continuation of medication and without dose reduction; approximately two third resolved with cessation or reduction of the drug. The majority of these cases took place with concomitant use of valproate and to a lesser degree, clobazam. In patients taking an oral solution at a dose of 10mg/kg/day, there was a 1% risk of elevated transaminase levels (elevated three times the upper normal limit), compared with 17% taking a dose of 20mg/kg/day.¹⁶ These dosages are significantly higher than our planned dosages.

Other serious side effects include suicidal ideation and this would result in removal from the study. Less common effects include weight loss, decreases in hemoglobin and hematocrit, and a reversible increase in creatinine in healthy adults.¹⁶

Risk of Norethindrone: Serious adverse reactions with the use of norethindrone are: (1) stroke (2) deep vein thrombosis (3) pulmonary embolism (4) myocardial infarction (5) retinal vein thrombosis. Adverse reactions commonly reported by norethindrone users are: irregular uterine bleeding, nausea, breast tenderness, and headache. Worsening or persistent migraines will result in cessation of study drug.

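### The Visit 2–5 symptom review names liver symptoms and NETA harms but none of the other seven common CBD effects, and no pre-dose stool frequency is specified, so symptomatic tolerability may be under-recorded

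*Combined protocol and SAP*

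**What the plan says.** Section 7.2.3 sets the schedule: "A physical assessment will be performed at visits #2-5, following the detailed history and physical examination performed at the screening visit". It introduces the content with "This assessment will include, but is not limited to". The second item is the "Detailed, but directed review of systems that will include symptoms concerning for liver disease, stroke, new/worsening migraine, deep venous thrombosis (DVT), pulmonary embolism (PE"), with new visual abnormalities added in the next sentence. The other items are vital signs, a directed examination that includes the mouth, a concomitant medication review, and "Adverse event assessment. Please refer to Section 3.3.1".

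Section 10.0 says: "Common risks of Cannabidiol include decreased appetite, somnolence, fatigue, sleep disorder (insomnia), diarrhea, hypersensitivity reactions (rash), infection and liver dysfunction". For the background drug it says: "Serious adverse reactions with the use of norethindrone are: (1) stroke (2) deep vein thrombosis (3) pulmonary embolism (4) myocardial infarction (5) retinal vein thrombosis". Sections 7.4.2 and 7.4.5 give NETA to every arm, open label. The randomised contrast is 0, 10 or 20 mg of CBD daily.

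Section 3.3.1 withdraws subjects for CTCAE Grade 3 events attributable to study drug. Its diarrhea example is an increase of at least "7 stools per day over baseline". Where causality cannot be determined, the event is attributed to study drug.

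The diary items named in Section 7.2.3 are pain score, adherence, rescue analgesics and menstrual pattern. Section 7.1 adds further daily parameters without naming them. Section 9.3 says adverse event forms will be developed; their content is not shown.

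**The concern.** The named prompts point mainly at harms of a drug that does not differ between arms. Most of the common symptoms that CBD could cause, and that could differ between 0, 10 and 20 mg, are left to general questioning whose wording is not fixed. General questions tend to pick up fewer mild symptoms than specific ones, and answers can vary with the assessor and the visit.

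Baseline is the second issue. Women with endometriosis pain may already have fatigue, poor sleep or bowel symptoms. Unless the same items are asked before the first dose, it is harder to say later whether a symptom is new or worse. The diarrhea example depends directly on such a baseline. Each subject withdrawn on an uncertain change is 1 of 12 in her arm, or 8%.

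At stake is the descriptive tolerability record of a pilot that Sections 2.2 and 8.2 intend as the basis for larger studies.

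**Working it through.** This is mainly a comparison of texts. The arithmetic only illustrates possible size.

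**Step 1: the two lists.** Section 10.0's common CBD effects against the items named in Section 7.2.3:

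| CBD effect (10.0) | Named in the Visit 2–5 review of systems? | Named elsewhere? |
|---|---|---|
| Decreased appetite | No | No visit or diary item |
| Somnolence | No | No visit or diary item |
| Fatigue | No | No visit or diary item |
| Insomnia | No | No visit or diary item |
| Diarrhea | No | Only as the Grade 3 example in 3.3.1 |
| Rash | No | Only in the allergic-reaction advice in 10.0 |
| Infection | No | No visit or diary item |
| Liver dysfunction | Yes | LFTs at Visits 1, 3, 4 and 5 |

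So 1 of 8 is prompted by name and 7 of 8 are not. The remaining prompts are stroke, migraine, DVT, PE and visual change. They match NETA's serious harms in 10.0 and the migraine rule in 3.3.1.

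**Step 2: does the cross-reference fill the gap?** The adverse event item in 7.2.3 points to 3.3.1. That section names thromboembolic events, migraine, suicidal ideation, liver dysfunction, and anemia and diarrhea at Grade 3. It does not name appetite loss, somnolence, fatigue, insomnia, rash or infection.

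**Step 3: baseline stool frequency.** The schedule in 7.2, the visit descriptions in 7.2.2 to 7.2.6 and the named diary items contain none.

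**Step 4: arm size.** Section 8.2 gives 36 participants and Section 7.2.3 gives 1:1:1 allocation, so 36 / 3 = 12 per arm, in line with the figure of 12 on which 8.2 relies.

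**Step 5: illustration.** Let p be the true proportion of an arm with a given effect and v the proportion of those cases that get recorded. The documents give neither, so both are assumed. Expected recorded cases are 12 × p × v, and the chance of recording none is (1 − p × v)^12.

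| p | v = 1 | v = 0.5 | v = 0.25 |
|---|---|---|---|
| 10% | 1.2 cases; 0.90^12 = 28% | 0.6; 0.95^12 = 54% | 0.3; 0.975^12 = 74% |
| 20% | 2.4; 0.80^12 = 7% | 1.2; 0.90^12 = 28% | 0.6; 0.95^12 = 54% |
| 30% | 3.6; 0.70^12 = 1% | 1.8; 0.85^12 = 14% | 0.9; 0.925^12 = 39% |

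The column v = 1 is an ideal. A checklist would not reach it exactly, and the present assessment may do better than v = 0.5.

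**Step 6: effect on a contrast between arms.** Assume true rates of 10% on placebo and 30% on high dose, with the same v in both. The recorded difference is (0.30 − 0.10) × v, which is 20, 10 and 5 percentage points for v = 1, 0.5 and 0.25. Approximate power with 12 per arm (normal approximation, two-sided 5%) is 22%, 12% and 8%. It is low even when every case is recorded.

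**The case against.** The strongest reply is that the protocol does look for adverse events actively. The list in 7.2.3 is open-ended, and a separate adverse event assessment takes place at the same visits. Section 3.3.1 requires evaluation for negative reactions at each visit, 7.1 requires screening for side effects, and 9.2 obliges the team to assess throughout. The forms and the unnamed diary parameters are not shown and could contain these prompts. This stands. It means the text permits specific questions without requiring them, and it rules out any claim that these effects go unassessed.

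Four stronger readings are tempting, and the documents do not support them.

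- A reader might infer that tolerability is under-counted. That cannot be shown without the forms or any detection rate. The statement in 9.2 that "Mild intensity events may or may not be volunteered by the patient" does not prove it either: it defines an intensity grade and does not describe how events are collected.
- A reader might infer that the diarrhea criterion cannot be applied. Usual bowel habit can be taken from the Visit 1 history, at Visit 2 or by recall, and an increase of seven or more stools a day is large enough to recognise. What is missing is a specified baseline record.
- A reader might infer that CBD's harms are not monitored. LFTs and the C-SSRS are done at Visits 1, 3, 4 and 5, CBC and BMP at screening and week 8, and the mouth is examined at Visits 2 to 5.
- A reader might infer a bias in favour of one arm. Assessment is blinded and identical across arms, so any shortfall should be roughly equal. It would shrink counts and absolute differences in all arms.

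It is also fair to say that tolerability by dose is neither an aim nor a listed endpoint; Section 1.3 only says that side effects will be monitored.

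**Conclusion.** The point holds as a limited gap in how symptoms are ascertained. Seven of the eight common CBD effects in Section 10.0 have no named prompt at Visits 2 to 5, and the diarrhea example in 3.3.1 has no specified pre-dose stool frequency. Those effects rely on unstandardised questioning, may be under-recorded, and are harder to separate from symptoms that were already there. Serious and laboratory risks of CBD are outside the gap.

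The size is unknown. The 7% against 28% chance of recording no case (true rate 20%, all against half elicited) rests wholly on assumed rates, and it treats a checklist as complete. The conclusion also assumes that the forms, which are not shown, do not already contain these items; if they do, the remaining task is to say so in 7.2.3.

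This is a cheap improvement worth making. Item-level baseline data that were not collected before dosing cannot be fully recovered later.

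**What to change.** In Section 7.2.3, under the physical assessment:

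- Add fixed yes/no items, each with a severity grade, for appetite, somnolence, fatigue, insomnia, diarrhea, rash and infection.
- Ask them at Visit 2 before the first dose and repeat them in the same words at Visits 3, 4 and 5. Study drug is dispensed at Visit 2 for use at bedtime, so the visit itself can serve as the pre-dose record.
- Record usual stools per day at Visit 2, as the baseline to which 3.3.1 refers.
- In Section 8.3, state that these effects will be reported descriptively by arm as new or worsened since Visit 2.

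No dose and no removal rule changes. The cost is one short REDCap form at visits that already include a review of systems, with no new tests. The downsides are slightly longer visits and more mild events recorded in all arms. The results stay descriptive, because 12 per arm cannot support a formal comparison of 10 and 20 mg.

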7.2.4 Study Visit 3 – 4 week treatment

The subject will return in 4 weeks for a follow up visit. The study visit window will be 3 days before or 3 days after this time to account for weekends. At this time the subject will be given time to ask any questions or voice any concerns they may have had over the past 4 weeks, reviewing and recording any adverse events. The subject's compliance with daily surveys and study drug will be reviewed.

A physical assessment will be performed as detailed in Section 7.2.3. Subjects who experience severe adverse events will be instructed to stop the study drug and withdraw from the study. Please refer to Section 3.3.1.

The subject will be given another 1 month supply of the study drug and NETA as needed. As stated above, NETA dosage will be adjusted as necessary.

The subject will also complete the following surveys: (1) EHP-30 (2) PGA (3) PGIC (4) C-SSRS (5) FSFI (if partnered and sexually active) on-site prior to being discharged from the visit. The following bloodwork will be obtained: (1) Inflammatory markers (2) Monitoring LFTS. Approximately 1-2 teaspoons of blood will be drawn at this visit.

They will be required to bring all medication bottles to the visit. Oxycodone, if prescribed, and NETA pills will be counted and recorded. Additional refills will be provided as needed. The study drug bottle and NETA will be inspected and returned to the clinician. The patient will be provided with a new supply of study drug and NETA at this time.

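### Suicidal ideation requires immediate removal, but the C-SSRS is not given at randomisation and ideation is missing from the symptom lists, so ideation first found at week 4 may not be placed before or after the first dose

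*Combined protocol and SAP*

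**What the plan says.** **Removal rule.** Section 3.3.1 states: "Known severe adverse events of the study drugs will result in the immediate cessation of the study drugs and removal from the study". For CBD it names two events: "1) Suicidal ideation (2) Liver Dysfunction resulting in hepatic failure", the second continuing with other forms of liver damage. Section 10.0 repeats the consequence: "Other serious side effects include suicidal ideation and this would result in removal from the study".

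**Entry rule.** Exclusion 11 in Section 3.2 bars women with suicidal ideation in the preceding year. Section 7.2.3 allows randomisation at Visit 2 only when every enrolment criterion is met.

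**Structured measurement.** At Visit 1 (Section 7.2.2): "Suicidal ideation will be assessed via the Columbia-Suicide Severity Rating Scale (C-SSRS". At Visit 3 (Section 7.2.4) the surveys are "1) EHP-30 (2) PGA (3) PGIC (4) C-SSRS (5) FSFI (if partnered and sexually active) on-site", and Sections 7.2.5 and 7.2.6 list the same set for weeks 8 and 12. For Visit 2, Section 7.2.3 says only: "At the enrollment visit, baseline study surveys and VAS scores will be collected".

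**Symptom lists.** The patient education text in Section 7.2.3 says "If they have any of the following, they will be advised to stop the medications and contact the study investigator" and then gives eight symptoms, all physical. The review of systems for Visits 2–5 names "symptoms concerning for liver disease, stroke, new/worsening migraine, deep venous thrombosis (DVT), pulmonary embolism (PE" and visual abnormalities.

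**General routes.** The Visit 2–5 assessment in Section 7.2.3 is open-ended and contains an adverse event assessment that points to Section 3.3.1. Section 3.3.1 also has women evaluated at each visit and advised to contact the team at once about new symptoms.

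**The concern.** A rule of immediate removal works only as well as the means of finding the event, and a safety comparison between arms needs a measurement taken just before dosing. Three things are at stake.

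- **Eligibility.** The only structured check of exclusion 11 comes before the run-in. NETA may be started at that same visit (Section 7.2.2), so a woman's treatment can change between the check and randomisation. Someone who has become ineligible could be randomised.
- **Attribution.** Ideation that begins between Visit 1 and the first dose may first show on the week-4 C-SSRS, where it would look like an on-treatment event. Section 18.3 counts an event of unknown and questionable relationship as drug-associated for reporting.
- **Data.** Under Section 3.3.2 a withdrawn woman contributes no further data and is not replaced. With 36 women randomised 1:1:1, each arm has 36/3 = 12, so one removal is 1/12 = 8.3% of an arm.

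**Working it through.** The plan states no figure on this point, so there is none to reproduce. The check is a cross-reading of the schedule followed by day counts.

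**1. Is the C-SSRS scheduled at Visit 2?**
The column alignment of the Section 7.2 table is broken in the text available, so the row was read against the visit sections.
- The C-SSRS row has the same pattern of marks as the LFT row: one mark, a gap, then three. Sections 7.2.2 and 7.2.4–7.2.6 place LFTs at Visits 1, 3, 4 and 5, and name the C-SSRS at the same four visits.
- Section 7.1 lists the week-0 surveys as EHP-30, PGA and, where applicable, FSFI. The C-SSRS is not among them, so the unnamed baseline surveys at Visit 2 do not supply it.

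**2. How long is the interval that contains the first dose?**
Inputs, with day 0 = Visit 2 and the first dose assumed to be taken that day:
- Visit 1 to Visit 2: 1–2 weeks = 7–14 days (Section 7.2.3).
- Visit 3: 28 ± 3 = day 25–31 (Section 7.2.4). Visit 4: 56 ± 3 = day 53–59. Visit 5: 84 ± 3 = day 81–87.
- NETA for 30 days before Visit 2 (Sections 7.2.1 and 7.2.3), possibly first started at Visit 1 (Section 7.2.2).

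Gap = (Visit 1 to Visit 2) + (Visit 2 to Visit 3). Pre-dose share = (Visit 1 to Visit 2) / gap.

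| Case | Shortest gap | Longest gap | Pre-dose share, lowest to highest |
|---|---|---|---|
| Stated 1–2 weeks | 7 + 25 = 32 days | 14 + 31 = 45 days | 7/38 = 18% to 14/39 = 36% |
| NETA started at Visit 1, Visit 2 exactly 30 days later | 30 + 25 = 55 days | 30 + 31 = 61 days | 30/61 = 49% to 30/55 = 55% |

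The second case is a minimum, because Visit 2 could fall later than day 30 of NETA. It also shows that the 1–2 week interval and the 30-day lead-in cannot both be met when NETA starts at Visit 1.

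**3. Which findings are ambiguous?**
- First positive at Visit 3: onset may lie on either side of the first dose.
- First positive at Visit 4 or 5 after a negative Visit 3: clearly after the first dose. These later intervals are 53 − 31 = 22 to 59 − 25 = 34 days for Visits 3–4, and 81 − 59 = 22 to 87 − 53 = 34 days for Visits 4–5.

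**4. Are the lists aligned with Section 3.3.1?**

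| CBD removal event | Eight-symptom list | Named review-of-systems items |
|---|---|---|
| Liver dysfunction | touched by severe abdominal pain | liver disease named |
| Suicidal ideation | nothing | nothing |

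**5. Effect of a C-SSRS at Visit 2.** The interval after the last pre-dose measurement becomes 25–31 days, all of it after dosing starts. Later gaps do not change.

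**The case against.** The strongest reply is that ideation is not left to chance.

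- The adverse event assessment at Visits 2–5 refers to Section 3.3.1, where ideation is named, and the assessment is not confined to its listed items. Adverse events are reviewed at Visits 3 and 4, women are educated on possible adverse events, and Section 9.8 provides round-the-clock cover by a licensed professional. The consent form was not available, so what it tells women about ideation is unknown. All of this stands. It rules out a reading that a reader might draw, namely that ideation can be neither caught promptly nor dated. What these routes do not supply is a structured pre-dose measurement or a named prompt between visits.
- A history taken at Visit 3 might date the onset, and Section 9.2 asks for enough detail to judge causality. The C-SSRS version and recall period are not stated, so the documents do not settle this either way. The supportable wording is that onset may not be datable.
- LFTs, which monitor the other CBD removal event, follow the same visits. That is true, and it shows that the schedule is consistent. But liver symptoms appear in the lists and ideation does not, and surveys are already completed at Visit 2.

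Three further inferences are tempting and not supported. First, the Section 3.3.1 sentence that attributes Grade 3 events to study drug when causality is undetermined concerns other adverse events. Ideation is on the named list and leads to removal without that step, so the sentence cannot cause a wrongful removal. Section 18.3 also lets the investigator record an event of unknown cause as unrelated, with reasons. Second, adding the repeat diary week to a full two weeks would give 21 days before dosing and a gap of 52, but no section says that the repeat extends the 1–2 week interval. Third, 8.3% is the weight of one case and not an expected frequency; exclusion 11 should make cases uncommon, and the analysis is primarily descriptive.

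**Conclusion.** The point holds in a limited form. There is no structured suicidality measurement at randomisation, although recent ideation is an exclusion and new ideation requires immediate removal. The unmeasured interval around the first dose is 32–45 days on the stated windows, of which 18–36% precedes dosing; it is at least 55 days when NETA is first started at Visit 1 and the lead-in is honoured. The ambiguity of onset is confined to ideation first found at Visit 3. Separately, the between-visit symptom list and the named review-of-systems items do not match the removal criteria. Between visits, detection therefore rests on general advice, and at visits it rests also on the adverse event assessment.

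This assumes that the first dose is taken on the day of Visit 2, that visits keep to their windows, and that the schedule table is read as set out in the working. It is a cheap improvement to safety data and eligibility checking, and it does not affect the primary pain comparison unless a case occurs.

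**What to change.** 1. **Schedule and Section 7.2.3:** add the C-SSRS at Visit 2, completed before randomisation with the surveys already given there. Use it to recheck exclusion 11 and as the pre-dose baseline for the later assessments. Cost: a few minutes per woman and an occasional extra screen failure. It does not shorten the time to the first on-treatment C-SSRS, which stays at day 25–31.
2. **Sections 3.3.1, 7.2.3 and 10.0:** reconcile the eight-symptom list and the named review-of-systems items with the protocol's own removal criteria, without introducing any new stopping criterion. Cost: an edit to the education sheet and the assessment form.
3. **Sections 7.2.1–7.2.3:** reconcile the 1–2 week interval with the 30-day NETA lead-in for women who start NETA at Visit 1, since the length of the gap depends on it. Cost: a wording change.
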